6.2.1 Screening Evaluation Consenting Procedure

As described in section 4.3, initial eligibility will be determined based on available clinical and claims data under a waiver of HIPAA Authorization.

Project assistants will serve as scheduling coordinators for the pilot study. Dyads who do not opt out (and those who opt in) will be called by the project assistant approximately 14 days after the study materials are mailed. Using the same approach that clinic staff use to call patients with dementia on the phone and identify their care partners during the course of clinical care, the project assistant will use an IRB-approved script (attached) to describe the pharmacist consult and assess interest. If the patient declines to identify a care partner and does not have a care partner listed in the EHR, the dyad will not be eligible. This phone call is described in section 4.3.

Participation in the pharmacist consult is not contingent on completion of the secondary outcome measure, FCMAHS. After scheduling the pharmacist consult, project assistants will offer care partners the option of completing the FCMAHS. They will obtain verbal consent for the FCMAHS when administering it over the phone (see script). If the care partner cannot complete the FCMAHS over the phone during the scheduling phone call,

the project assistant will offer to call back before the pharmacist visit (up to 28 days) or to later e-mail them a link to an electronic version.

6.2.2 Enrollment, Baseline, and/or Randomization

Enrollment

Project assistants will mail study materials with opt-out provisions to the homes of 60 patients (30 at each site). Dyads who do not opt out (or who opt in) will be called by the project assistant approximately 14 days later to describe the pharmacist consult and assess interest. Enrollment will be defined as the date of this phone call.

Baseline Assessments

The baseline point will be defined as the date of the enrollment phone call, whether or not dyads are randomized to the intervention or delayed intervention control group.

Randomization

Dyads who do not opt out (or who opt in) will be randomized to the immediate or delayed intervention group prior to the enrollment/scheduling phone call using computergenerated random numbers. The intervention group will be scheduled to have the pharmacist telehealth visit immediately (within 4 weeks) after enrollment. The delayed intervention group will receive the pharmacist-led component 3-4 months after enrollment. For dyads randomized to the delayed group, the project assistant will say, "I will call you back in about 3 months to remind you of the call with the pharmacist."

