4.2 Exclusion Criteria

Candidates meeting any of the following exclusion criteria at baseline will be excluded from study participation:

- As both the pilot and the planned pragmatic trial will be based in primary care, individuals residing in long term care facilities or enrolled in hospice will be excluded.
- Individuals who cannot converse comfortably in English will be excluded because the FCMAHS has not been validated in other languages.

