4.3 Study Enrollment Procedures

1) Using clinical and claims data under a waiver of HIPAA Authorization, the data analytics team at each institution will identify all patients at each of the two clinics who meet inclusion criteria. This list will be routed to the project assistant via a HIPAA-compliant method.

2) The project assistant will perform administrative roles for the study. This includes: Mailing study materials with opt-out provisions to the homes of 30 randomly selected patients from this list. Patients will be entered into a study database for tracking and to avoid repeated mailings. Study materials will include a phone number that patients or care partners can call to opt out. We will continue mailing materials to eligible patients until 30 have been recruited at each clinic. Materials will also provide dyads the opportunity to opt *in* by calling the phone number. To emphasize that the study is for care partners, the envelope and introductory letter will be addressed to the patient and family (eg, "[name] and family").

Scheduling virtual visits with the clinical pharmacist. Dyads who do not opt out (and those who opt in) within 14 days of the study mailing will be randomized using computer-generated random numbers to either the intervention group or the delayed intervention control group, and called by the project assistant.

If the patient and care partner do not opt out, the project assistant will call the patient's phone number listed in the EHR and use an IRB-approved script (attached) to identify the care partner:

- The project assistant will briefly explain that they are calling about "a program for family members and friends who are caring for someone with memory problems."
 - If the patient answers the phone, the project assistant will say, "I'm calling about your medicines. Many people have someone who helps them manage their medicines on a daily basis." They will then ask to speak with the care partner.
 - If the care partner answers the phone, the project assistant will ask, "Are you the person who helps [PATIENT] the most to manage their medicines?"

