 This is the standard approach that clinic staff use to call patients with dementia on the phone and identify their care partners during the course of clinical care. As the intervention is designed to address the needs of care partners and requires their participation, the project assistant will ask to speak with the care partner first. Because some patients with mild or moderate dementia may be interested in hearing about the program, the project assistant will offer to describe it to the patient as well.
- Patients who are unwilling or unable to identify a care partner who helps them manage their medicines will be excluded. The project assistant will document the reasons for ineligibility in a REDCap Screening Log.
- The project assistant will briefly describe the pharmacist consult to the care partner. If the care partner agrees, the project assistant will schedule the pharmacist call, which will occur immediately (within 4 weeks) for the intervention group and at approximately 3 months for the delayed intervention control group.

4) If patients or care partners opt out during the phone call, the project assistant will document the reason (eg, no time to participate, not interested) in a REDCap Screening Log.

5) Dyads randomized to the delayed intervention group will be told that they will receive another phone call from the project assistant in approximately 3 months to remind them of their appointment with the clinical pharmacist.

6) After scheduling the pharmacist consult, project assistants will offer care partners in both groups the option of completing the secondary outcome measure, the Family Caregiver Medication Administration Hassles Scale (FCMAHS). For care partners who are interested in completing the FCMAHS, project assistants will obtain verbal consent when administering the measure over the phone (see script). If the care partner does not wish to complete the FCMAHS over the phone during the scheduling phone call, the project assistant will offer to call back before the pharmacist visit (up to 28 days) or to later e-mail the care partner a link to an electronic version.

5 STUDY INTERVENTIONS

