9.2.1 Treatment Assignment Procedures

Enrolled dyads will be randomized prior to the scheduling phone call using computer-generated random numbers to either the intervention group or the delayed intervention group. The intervention group will then be scheduled to have the pharmacist telehealth visit immediately (within 4 weeks) after enrollment. The delayed intervention group will be scheduled to receive the pharmacist-led component 3-4 months after enrollment. For dyads randomized to the delayed group, the project assistant will say, "I will call you in about 3 months to remind you of your appointment with the pharmacist." Due to the nature of the intervention, participants, pharmacists and PCPs cannot be masked. Project assistants will enter data into a REDCap database so that the researchers can analyze it without having access to group assignment.

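### Dyads are randomised before the call that settles eligibility, agreement and the baseline FCMAHS, and the plan does not settle whether dyads lost at that call stay in the analysis

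*Combined protocol and SAP*

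**What the plan says.** Three sections place randomisation before the scheduling call. Section 4.3: dyads who have not opted out within 14 days of the mailing, or who opt in, "will be randomized using computer-generated random numbers to either the intervention group or the delayed intervention control group, and called by the project assistant". Section 6.2.2: they "will be randomized to the immediate or delayed intervention group prior to the enrollment/scheduling phone call". Section 9.2.1: "Enrolled dyads will be randomized prior to the scheduling phone call".

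Section 6.2.2 also ties enrolment and baseline to that call: "Enrollment will be defined as the date of this phone call", and "The baseline point will be defined as the date of the enrollment phone call".

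Eligibility is partly settled on the call. Section 4.3: "Patients who are unwilling or unable to identify a care partner who helps them manage their medicines will be excluded", followed by "The project assistant will document the reasons for ineligibility in a REDCap Screening Log". Section 6.2.1 has a narrower rule: the dyad is ineligible only if the patient declines to name a care partner and the EHR lists none. Section 4.1 requires the care partner to be at least 21. Section 4.2 adds a language criterion whose stated reason is the care partner's questionnaire: "Individuals who cannot converse comfortably in English will be excluded because the FCMAHS has not been validated in other languages".

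On the same call the project assistant seeks agreement, logs refusals with reasons, and books the pharmacist visit within 4 weeks or at about 3 months according to arm. Sections 4.3, 5.1 and 6.2.1 place the baseline FCMAHS offer after that booking.

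For analysis, Sections 9.1 and 9.5 name intention to treat for Aim 2b, count all events after randomisation, treat analyses using post-randomisation data as secondary, and separate non-compliance from missing follow-up. They assess pMRCI change by assigned intervention, with multiple imputation.

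**The concern.** Two things follow from this order.

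First, exclusion and refusal at the call come after allocation. They are handled by a caller who must know the arm in order to book, and whom no section describes as masked; the masking in Sections 5.2 and 9.2.1 concerns the researchers analysing the data. A dyad offered a visit in three months may decline more or less readily than one offered a visit within four weeks. If dyads lost at the call leave the analysis, the arms compared are no longer the arms randomised.

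Second, the baseline FCMAHS is answered when the care partner already knows the date of the visit. The analysis uses change scores, so any effect of the known wait on baseline answers passes directly into the outcome.

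The pilot tests no statistical hypotheses, but it does plan arm comparisons of pMRCI and FCMAHS change, and their estimates and precision are meant to help plan the larger pragmatic trial. The planners of that trial need to know which randomised dyads the estimates describe.

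**Working it through.** **Which dyads are analysed.**
- Text that keeps dyads lost at the call: intention to treat for Aim 2b, the counting of all events after randomisation, and pMRCI analysis by assignment with multiple imputation (9.1, 9.5).
- Text that drops them: exclusion with entry in a screening log (4.3), ineligibility (6.2.1), and enrolment dated to the call (6.2.2).
- Section 9.2.1 speaks of enrolled dyads being randomised before the event that Section 6.2.2 defines as enrolment.
- Section 6.2.4 keeps EHR and VDW extraction after early discontinuation. Its example is opting out at the pharmacist call; the scheduling call is not mentioned.
- A dyad lost at the call is never offered the FCMAHS, the outcome of the one aim for which intention to treat is named.

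**The plan's precision figure.** Inputs from Section 9.2: 30 per arm, 10% attrition, SD 1, two-sided 95% interval, width 0.4 SD. Evaluable per arm: 30 × 0.9 = 27.
- One-arm half-width: t(0.975, 26)/√27 = 2.056/5.196 = 0.396. The stated 0.4 therefore reproduces as a half-width for one arm's mean.
- Between-arm half-width: t(0.975, 52) × √(2/27) = 2.007 × 0.272 = 0.546 SD. This is the benchmark for an arm comparison.

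**Loss at the call.** The documents give no rate, so L = 10% to 40% of randomised dyads is assumed.
- If mailing continues until 60 remain after the call, the number randomised is 60/(1 − L): 67, 75, 86 and 100 at L = 10, 20, 30 and 40%. Then 7, 15, 26 or 40 randomised dyads have an unsettled analysis status, and the half-width stays at 0.546.
- If 60 are randomised, evaluable per arm is 27 × (1 − L): 24.3, 21.6, 18.9 and 16.2. The between-arm half-widths are 0.577, 0.614, 0.660 and 0.717 SD.
- Section 4.3 continues mailing until 30 are recruited at each clinic, without tying recruited to randomisation or to the call. Section 6.2.2 speaks of mailing to 60 patients. Either case is possible.

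**Possible bias from refusal that differs by arm.** All inputs are assumed: refusal r_low of 10% to 20% in one arm, r_high 5 to 20 points higher in the other, and extra refusers whose mean change differs by d = 0.2 to 0.5 SD from that of dyads who would stay in either arm. Bias = d × (r_high − r_low)/(1 − r_low).
- Lowest: 0.2 × 0.05/0.90 = 0.011 SD.
- Middle: 0.5 × 0.10/0.90 = 0.056 SD.
- Highest: 0.5 × 0.20/0.80 = 0.125 SD.
- Against 0.546: 0.011/0.546 = 2% and 0.125/0.546 = 23%.

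**Cost of analysing all randomised dyads under the present order.** Assume no effect in dyads who never enter, 60 remaining after the call, and 10% attrition. Evaluable per arm is 27/(1 − L): 30.0, 33.8, 38.6 and 45.0. Half-widths are 0.517, 0.486, 0.454 and 0.419 SD. The estimate recovers a fraction 1 − L of the effect among dyads who enter, so dividing by 1 − L gives 0.574, 0.608, 0.648 and 0.698 SD on their scale.

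**The case against.** The strongest reply is that the plan already contains the principle. Intention to treat, taken at its word, includes everyone randomised; pMRCI is analysed by assignment; compliance-based analyses are secondary; and imputation is specified. That stands. A reader might infer that the plan adopts no intention-to-treat principle or openly discards these dyads, and the documents do not support that. The defect is that the exclusion and enrolment wording points the other way and is not reconciled.

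A reader might also infer that call-stage refusers appear nowhere in the analysis. That too goes too far: the opt-out proportion is an Aim 1 feasibility measure, and refusal reasons are logged. Section 6.1 schedules this measure at identification of the eligible population, however, so its coverage of refusals on the later call is unclear.

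A third tempting inference is that the arm comparison is materially biased. The mailing opt-out closes before randomisation (4.3). The cover letter tells all dyads beforehand of a possible wait of up to 3 months, described as usual care (11.2). Some care partners are already listed in the EHR (6.2.1). Refusal that differs by arm is possible, not shown.

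Finally, the planned trial is cluster randomised, where assignment ordinarily precedes individual contact, and booking before offering the FCMAHS supports the assurance that the consult does not depend on the questionnaire. Both are fair reasons for the present order. Neither settles the analysis set, and the second can be met by an explicit statement on the call.

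**Conclusion.** The concern holds. As written, the plan produces exclusions and refusals after randomisation and a baseline FCMAHS taken when the wait is known, and its sections disagree on whether the affected dyads are analysed. That much rests on the text alone.

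The size of any bias is not derivable from the documents. The range in the working rests wholly on assumed refusal rates and differences, and it suggests an effect that is probably small beside the pilot's own imprecision. It cannot be said that precision is unaffected, nor that it is lost: that depends on whether the 60 are counted at randomisation or after the call. A low-cost improvement should be made; the flaw does not invalidate the pilot.

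**What to change.** **Preferred.** Amend Sections 4.3, 5.1, 6.2.1, 6.2.2, 9.2.1 and 11.2 so that the same call runs in this order:
1. Confirm the care partner and eligibility under one rule, reconciling Section 4.3 with Section 6.2.1.
2. Obtain agreement to the consult.
3. Offer the baseline FCMAHS, stating that the consult does not depend on it.
4. Draw the arm from a concealed REDCap list by site.
5. Book the visit.

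Count the 60 from step 4. Analyse all of them by assigned arm for pMRCI and medication count, and report FCMAHS non-response by arm. Reconcile the use of enrolled in Section 9.2.1 with the definition in Section 6.2.2.

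The cost is a script revision with IRB re-approval and an allocation list, with no added staff or visits. There are three drawbacks. The FCMAHS offer moves ahead of booking, so the statement in step 3 must be explicit. Care partners who defer the FCMAHS to a call-back or e-mail link still answer knowing their date. Refusal prompted by the date can still follow the draw, but is then counted.

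**If the order must stay.**
- In Sections 9.1 and 9.5, define the pMRCI and medication-count set as all randomised dyads, and in Section 6.2.2 set their baseline at the randomisation date.
- In Section 6.2.4, extend EHR and VDW extraction to all of them, subject to IRB agreement.
- Define the FCMAHS set as randomised dyads whose care partner consented, and describe it as that, not as full intention to treat.
- Report call-stage exclusions, refusals and non-contacts by arm, including in the Aim 1 opt-out proportion.

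This alternative costs precision: about 0.57 to 0.70 SD on the scale of dyads who enter, under the assumptions in the working.

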- 2a) To determine the feasibility of measuring the primary outcome, the patient-level Medication Regimen Complexity Index (pMRCI)¹⁻⁴, within the existing EHR systems, and to compare it with a more pragmatic measure, chronic medication count, as the primary outcome measure for the ePCT.
- 2b) To determine the feasibility of measuring the secondary outcome, the Family Caregiver Medication Administration Hassles Scale (FCMAHS)⁵, a caregiver-reported outcome measure.

Design and Outcomes

This is a pilot study of a pragmatic intervention consisting of the following strategies: 1) direct-to-consumer deprescribing educational materials designed to activate the care partner and PLWD; 2) a telehealth visit in which a clinical pharmacist discusses benefits and harms of the patient's medications with the patient and care partner in the context of their goals and preferences; and 3) pharmacist-PCP communication in which the pharmacist provides tailored deprescribing recommendations designed to be useful and actionable for the PCP. The study will assess the feasibility and preliminary efficacy of the intervention in two healthcare systems, to guide the subsequent evaluation of the intervention in an ePCT.

Patient eligibility criteria will be: age ≥ 65 years with a diagnosis of Alzheimer's disease or related dementia (ADRD) from ICD-9 or ICD-10 visit codes or from the electronic health record (EHR) problem list and ≥ 5 chronic medications. Patients and care partners will be enrolled as dyads and randomized to the intervention group and a delayed intervention control group that will receive the pharmacist-led component 3 months after the educational mailing.

Interventions and Duration

Dyads at each pilot site will be randomly assigned to receive the pharmacist-led intervention immediately after the educational mailing or to a delayed intervention control group that will receive the pharmacist-led component 3 months after the mailing. Piloting with a delayed intervention control group will allow for a more realistic examination of the differential effect of a low-touch control arm (educational mailing only) vs. the pharmacist-led process. Each participant will be on study (intervention period and additional follow-up) for 3 months.

Sample Size and Population

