The proposed pragmatic intervention consists of the following strategies: 1) direct-toconsumer deprescribing educational materials designed to activate the care partner and PLWD; 2) a telehealth visit in which a clinical pharmacist discusses benefits and harms of the patient's medications with the patient and care partner in the context of their goals and preferences; and 3) pharmacist-PCP communication in which the pharmacist provides tailored deprescribing recommendations designed to be useful and actionable for the PCP. The study will assess the feasibility and preliminary efficacy of the intervention in two healthcare systems, to guide the subsequent evaluation of the intervention in an ePCT.

We will enroll 60 patients and their care partners as dyads (15 dyads per arm at each site). Patient eligibility criteria will be: age \geq 65 years with a diagnosis of ADRD from ICD-9 or ICD-10 visit codes or from the EHR problem list and \geq 5 chronic medications. In

Baltimore, the study site will be 1-4 clinics that are part of Johns Hopkins Community Physicians (JHCP). In Denver, the study sites will be KPCO greater Denver metro primary care practices. Dyads at each pilot site will be randomly assigned to receive the pharmacistled intervention immediately after the educational mailing or to a delayed intervention control group that will receive the pharmacist-led component 3 months after the mailing. (Please see the Consent section for a discussion of consent options for consenting patients as part of pragmatic trials.)

This protocol employs a pragmatic design. The intervention is delivered by clinical pharmacists who are already integrated in primary care clinics at JHCP and KPCO. The pharmacists are trained in complex geriatric medication management and routinely provide comprehensive medication management to Medicare beneficiaries.

Aim 1 is to assess the feasibility and acceptability of ALIGN in two different health care systems, to guide the subsequent evaluation of the effectiveness of the intervention in an ePCT. Data to measure feasibility will be acquired from the EHR, checklists completed by the pharmacists, and audiorecordings of pharmacist phone calls with care partners. We will collect the following measures:

• Proportion of dyads that opt out of the intervention;

• Proportion of pharmacist messages to the PCP that receive an acknowledgement or response;

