5) Using comprehensive medication management (CMM) as a foundation, the pharmacist will call the patient-care partner dyad to assess for medication-related problems, such as issues with adherence, potential adverse effects and caregiver strain related to medication management. Clinical pharmacists are already embedded in both pilot clinics and throughout their parent healthcare systems, and are conducting CMM phone calls with patients. The clinical pharmacists in ALIGN have considerable experience doing medication reviews with older adults, patients with dementia and care partners. They will use a script that was closely adapted from templates that are currently being used by embedded clinical pharmacists in both healthcare systems. The pharmacists will use these guiding questions to elicit the dyad's goals and priorities for the patient's health in

order to align medications with goals of care (see attached template). We anticipate that the intervention phone call will take up to 1 hour.

6) The pharmacist will then develop an evidence-based deprescribing communication, which will be routed to the PCP via the EHR using a standardized template (see attached). The pharmacist will contact the PCP as per usual clinical practice. The template will encourage the PCP to respond to the pharmacist either to accept the recommendations, to ask questions or to raise concerns.

7) With the PCP's approval, the pharmacist will call the dyad to implement the recommendations and document the changes in the EHR. An updated medication list will be mailed to the dyad. All decisions about discontinuation or continuation of medications will be made by the PCP and patient/ care partner.

Delayed intervention group:

Steps 1-2 will be identical to the intervention group. For participants randomized to the delayed intervention control group, the project assistant will schedule the pharmacist consult in approximately 3 months.

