After scheduling the pharmacist consult, project assistants will offer care partners in the delayed intervention group the option of completing the Family Caregiver Medication Administration Hassles Scale (FCMAHS). They will obtain verbal consent for the FCMAHS when administering it over the phone (see script). If the care partner cannot complete the FCMAHS over the phone during the scheduling phone call, the project assistant will offer to call back before the pharmacist visit (up to 28 days) or to later e-mail them a link to an electronic version. The FCMAHS will be administered again 3 months after the enrollment phone call.

The project assistant will call the care partner again closer to the date of the pharmacist visit to remind them of the appointment. Steps 4-6 will be identical the intervention group but will occur 3-4 months after study enrollment.

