6.1 Schedule of Evaluations

Assessment	Identify eligible population	Baseline: scheduling phone call (Day 0 + 28 days)	3 months post enrollment (Day 90 + 45 days)
Inclusion/Exclusion Criteria	X		
Patient demographics and diagnoses	X		
Care partner demographics		X	
Chronic medication count		X	X
Patient-level Medication Regimen Complexity Index (pMRCI)		X	X
Family Caregiver Medication Administration Hassles Scale (FCMAHS)		X	X

Feasibility measures			
Proportion of dyads that opt out	X		
Proportion of participants with data elements available to calculate pMRCI			·
		Throughout	intervention
Response rate and completion time for FCMAHS		Х	X
Proportion of pharmacist messages to PCP that receive			
acknowledgement or response		Throughout	intervention
Number of contacts between		Inoughout	
pharmacist and PCP and between pharmacist and dyad			
		Throughout	intervention
Time required by pharmacist to complete intervention			X
Type of recommendations made by pharmacist, acceptance rates for recommendations			X
Fidelity measures			
Proportion of intervention elements successfully completed by pharmacist			X

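### The 3-month outcome window stays open past the control arm's own pharmacist visit, and nothing requires control outcomes to be taken first

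*Combined protocol and SAP*

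**What the plan says.** The Précis (Interventions and Duration) gives the purpose of the delayed control: to examine the "differential effect of a low-touch control arm (educational mailing only) vs. the pharmacist-led process". It adds: "Each participant will be on study (intervention period and additional follow-up) for 3 months".

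The timing of the control arm's pharmacist visit is worded in three ways:

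- Section 6.2.2: "The delayed intervention group will receive the pharmacist-led component 3-4 months after enrollment". Sections 5.1 (end of the delayed-group text) and 9.2.1 agree.
- Section 4.3: "and at approximately 3 months for the delayed intervention control group". Section 5.1, at the start of the delayed-group text, has "the project assistant will schedule the pharmacist consult in approximately 3 months".
- Précis and Section 3: a "delayed intervention control group that will receive the pharmacist-led component 3 months after the mailing". The mailing precedes the enrollment call by about 14 days (6.2.2).

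The cover letter described in 11.2 adds that the consult may be up to 3 months out.

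For the outcomes, the Schedule of Evaluations (6.1) has one follow-up column for both arms, headed "3 months post enrollment (Day 90 + 45 days". The plus sign is underlined in the source, meaning plus or minus. The column covers chronic medication count, pMRCI and FCMAHS. Section 6.2.3 counts follow-up from the enrollment call. For the delayed group, Section 5.1 says: "The FCMAHS will be administered again 3 months after the enrollment phone call".

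The only wording that places a measurement before the pharmacist visit (4.3, 5.1, 6.2.1, 11.2) concerns the baseline FCMAHS. Sections 9.1 and 9.5 regress change in pMRCI and in FCMAHS on assigned arm and have no rule for control values obtained after the control visit.

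**The concern.** A delayed-intervention control serves as a control only until its own intervention begins. If a control dyad has already had the pharmacist call when its 3-month outcome is recorded, that outcome belongs partly to the intervention condition. An effective intervention would then look weaker in the pMRCI and FCMAHS change comparisons, which the plan wants for designing the later pragmatic trial. Because the researchers analyse the data without access to group assignment (5.2, 9.2.1), they would be unlikely to notice unless such values are marked.

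Medication count is less exposed. Section 9.4 plans only to measure its change, as an alternative outcome measure to pMRCI, and neither 9.1 nor 9.5 states a between-arm regression for it.

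**Working it through.** **Window.** 90 − 45 = 45 and 90 + 45 = 135, so days 45 to 135 after the enrollment call.

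**Days the window stays open after the control visit** (135 minus visit day, taking a month as 30 days):

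| Wording of control visit | Approximate day | Days remaining |
|---|---|---|
| 3 to 4 months after enrollment | 90 to 120 | 45 to 15 |
| Approximately 3 months | 90 | 45 |
| 3 months after mailing | 90 − 14 = 76 | 59 |

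Under every wording an in-window outcome can follow the visit.

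**Does any text close the gap?** The nominal order is outcome at 3 months and visit at 3 to 4 months, which points the right way. Three things stop it from being a rule:

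- An on-target day-90 outcome can coincide with a visit at about 3 months.
- The same 3-month column holds pharmacist time, recommendations and fidelity. For controls these exist only after the visit, so the column cannot be read as a pre-visit time point.
- Section 5.1 says that steps 4 to 6 take place at 3 to 4 months for controls. In the numbered list, step 4 is the FCMAHS and the pharmacist-led steps are 5 to 7, so the control sequence is itself unclear.

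**Share of control outcomes after the visit.** The documents give no distribution of dates, so everything here is assumed. Let V be the visit day, uniform on 90 to 120 unless stated, and L the lag in days before changes show.

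- All data cut at day 90: 0%.
- Outcome day uniform on 45 to 135, independent of V: mean of max(0, 135 − V − L)/90. With L = 0, (135 − 105)/90 = 33%. With L = 14, (121 − 105)/90 = 18%. With L = 28, 5%.
- Outcome day triangular, peaked at 90: mean of max(0, 135 − V − L)²/4050. With L = 0, 975/4050 = 24%. With L = 14, 331/4050 = 8%. With L = 28, 1%.
- Outcome day uniform but correlated with V (Gaussian copula, 2,000,000 draws): correlation 0.5 gives 31% with no lag and 12% at 14 days; correlation 0.8 gives 29% and 7%.
- All visits at day 90, outcome day uniform, no lag: 45/90 = 50%. With a 14-day lag, (135 − 104)/90 = 34%.

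**Dilution.** If a fraction f of analysed controls carries the full intervention effect, the contrast shrinks to (1 − f) of its true size, so each late control costs 1/n. With 30 × 0.9 = 27 controls (9.2), that is 1/27 = 3.7%. FCMAHS is optional, so its n may be smaller; with 20 respondents (assumed) it is 1/20 = 5%.

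These are upper bounds if a control's effect soon after its visit is no larger than the intervention arm's at follow-up. The intervention visit is within 28 days of enrollment, so at day 90 that arm is 90 − 28 = 62 to 90 days past it. A control seen on days 90 to 120 is at most 45 days past its visit when the window closes.

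**The case against.** The strongest reply is that the order is already implied: follow-up is targeted at 3 months throughout, the procedural sections put the control visit at 3 to 4 months, and participants are on study for 3 months. EHR and VDW data can be dated to day 90 without redesign, so the practical exposure is mainly FCMAHS. Recommendations also need a PCP message, PCP approval and a second call before anything changes, so a value taken days after the visit may carry little effect. This stands as a limit on size. It does not supply the missing rule, because the window expressly permits later values.

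A second reply is that Sections 9.1 and 9.5 state no statistical hypotheses, focus on precision, and already treat analyses using post-randomization data as secondary. A few late controls shift a mean difference more than they alter its precision. That lowers the stakes, but the Précis and Section 3 also speak of preliminary efficacy, and the arm comparison is planned. The call scripts are external documents, so any ordering instruction in them cannot be checked here.

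A reader might infer three stronger things that the documents do not support:

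- That the plan schedules control outcomes after the visit. It permits this; the nominal schedule points the other way.
- That about a third of control outcomes will be affected. That figure comes from assumed dates and is neither an expectation nor a ceiling.
- That the pilot's main purpose is compromised. The feasibility and acceptability measures do not depend on this contrast.

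**Conclusion.** The point holds as a gap in the plan: the stated window and the stated visit times are compatible with control outcomes taken after the control intervention, and no section prevents it. The window arithmetic is certain. The consequence is conditional: bias toward zero in the exploratory pMRCI and FCMAHS contrasts if the intervention works and if late values occur.

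The share affected cannot be known from the documents. With visits spread over days 90 to 120, it is 24% to 33% when outcome and visit days are independent and there is no lag, and 7% to 18% with a 14-day lag. It reaches 50% with visits at day 90 and no lag, and is nil with a day-90 cut. Severity is minor to moderate, and the correction is cheap.

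**What to change.** 1. Reconcile the control-visit wordings (Précis, Sections 3, 4.3, 5.1, 6.2.2, 9.2.1 and the cover-letter text in 11.2) with each other and with the outcome window in 6.1, and correct the step cross-reference in 5.1. This review does not choose the visit schedule.
2. State that control 3-month outcomes precede the control pharmacist visit. Extract pMRCI and medication count in both arms as of one common fixed day after enrollment that falls before that visit.
3. Close the 3-month FCMAHS on the same day after enrollment in both arms, before the control visit. Use the same type of contact in both arms; the reminder call is made only to controls, so using it would give the arms different contact contexts.
4. Flag any control value obtained after the visit and exclude it in a sensitivity analysis.
5. Continue to count late FCMAHS forms in the Aim 2b response rate.

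The cost is wording in a few sections and a dated extraction from the EHR and VDW. The downside is that a few late FCMAHS forms, in either arm, become missing for the effect estimate. The timing of the e-mailed baseline FCMAHS, which lacks the before-visit condition attached to the phone call-back, is a separate minor point.
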